4.3 Study Drug Handling

Current ICH GCP Guidelines require the Investigator to ensure that study drug deliveries from the Sponsor are received by the Investigator/or designee and that:

- Such deliveries are recorded;
- Study drug is handled and stored according to labeled storage conditions;
- Study drug with appropriate expiry/retest only is dispensed to study subjects in accordance with the protocol, and;
- Any unused study drug is returned to the Sponsor, unless prior approval is received from the Sponsor allowing local standard procedures for the alternative disposition of unused study drug.

Study drug inventory and accountability records for the study drugs will be kept by the Investigator. Study drug accountability throughout the study must be documented and reconciled. The following guidelines are therefore pertinent:

- The Investigator or designee agrees not to supply study drugs to any persons except the eligible subjects in this study in accordance with the protocol.
- The investigator, head of study site or designee will keep the study drugs in a pharmacy or other locked and secure storage facility under controlled storage conditions, accessible only to those authorized by the investigator to dispense these study drugs.
- A study drug inventory will be maintained by the investigator, head of study site or designee. The inventory will include details of material received and a clear record of when they were dispensed and to which subject.
- At the conclusion or termination of this study, the Investigator or designee agrees to conduct a final drug supply inventory and to record the results of this inventory on the Drug Accountability Record. It must be possible to reconcile delivery records with those of used and/or returned medication. Any discrepancies must be accounted for and documented. Appropriate forms of deliveries and returns must be signed by the site staff delegated for this responsibility.
- The site staff must return study drug to the sponsor or designee at the end of the study or upon expiration unless otherwise approved by the sponsor.

4.4 Blinding

This section is not applicable as this is an open label study.

4.5 Assignment and Allocation

Subjects will be entered into the IRT system at screening and assigned a subject number. Randomization will be not performed as this is single-arm study.

5 TREATMENTS AND EVALUATION

5.1 Dosing and Administration of Study Drug(s) and Other Medication(s)

5.1.1 Dose/Dose Regimen and Administration Period

Study drug consists of enzalutamide provided as 40 mg capsules to be taken as 160 mg (4 capsules) orally once daily. Study drug is to be taken until disease progression, unacceptable toxicity or any other discontinuation criteria are met.

Study drug will be self-administered at home by the subject and taken as close to the same time each day as possible. Study drug can be taken with or without food. Subjects should not make up missed or vomited doses; dosing should resume the following day unless otherwise instructed.

5.1.2 Increase or Reduction in Dose of the Study Drug(s)

During the study, subjects who experience a National Cancer Institute (NCI)-Common Terminology Criteria for Adverse Events (CTCAE) guidelines (version 4.03) grade 3 or higher AE (except liver function test [LFT] AE) toxicity that is attributed to the study drug and cannot be ameliorated by the use of adequate medical intervention and/or dose reduction may interrupt study drug treatment for 1 week or until the toxicity grade improves to grade 2 or lower in severity. Study drug may be restarted at the original dose (160 mg/day) or a reduced dose (120 mg or 80 mg/day). If restarted at a lower dose or if interrupted for > 2 weeks, the Medical Monitor must be consulted. After dose reduction, based on subject tolerance, study drug may be increased to a maximum dose of 160 mg/day per Investigator discretion.

Enzalutamide must be interrupted during the evaluation of symptoms suspicious of PRES (headache, lethargy, confusion, blindness and other visual and neurological disturbances, with or without associated hypertension).

5.1.3 Previous and Concomitant Treatment (Medication and NonMedication Therapy)

Medications taken within 28 days prior to the screening visit and up to the first dose of study medication will be documented on the appropriate case report form (CRF) as a prior medication.

Medications taken after the first dose of study medication up until the final follow-up visit will be documented on the appropriate CRF as concomitant medication.

Prior and concomitant medications include all vitamins, herbal remedies, over the counter, and prescription medications.

5.1.3.1 Required Concomitant Treatment

All subjects are required to receive background therapy with ADT, either bilateral orchiectomy or a GnRH agonist or antagonist, which must be maintained during study treatment, as per standard of care (SOC).

A GnRH agonist or antagonist will be provided from the site's stock and administered in accordance with prescribing information.

5.1.3.2 Prohibited Concomitant Treatment

A list of excluded concomitant medications is provided in [Appendix 12.1 List of Excluded Concomitant Medications]. The following medications are prohibited within 4 weeks of day 1 and during the study treatment period:

- 5 α-reductase inhibitors (finasteride, dutasteride);
- Estrogens;
- Cyproterone acetate;
- Abiraterone
- Biologic or other agents with antitumor activity against prostate cancer (with the exception of those therapies identified in inclusion/exclusion criteria);

- Systemic glucocorticoids greater than the equivalent of 10 mg per day of prednisone intended for the treatment of prostate cancer;
- Herbal medications that have known hormonal antiprostate cancer activity and/or are known to decrease PSA levels (i.e., saw palmetto);
- Androgens (testosterone, dehydroepiandrosterone, etc.);
- Investigational agents.

In addition, bisphosphonates and denosumab are prohibited unless stabilized for 2 weeks prior to day 1 and held constant throughout study treatment or administered for diagnosis of osteoporosis.

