Subjects who experience a grade 3 or higher toxicity that is attributed to the study drug and cannot be ameliorated by the use of adequate medical intervention and/or dose reduction may interrupt study drug treatment for 1 week or until the toxicity grade improves to grade 2 or lower in severity. Study drug may be restarted at the original dose (160 mg/day) or a reduced dose (120 mg or 80 mg/day). If restarted at a lower dose or if interrupted for > 2 weeks, the Medical Monitor must be consulted.

Other Treatment for Prostate Cancer during the Study:

ADT (Androgen deprivation therapy), either bilateral orchiectomy or GnRH agonist or antagonist, which must be maintained during study treatment. A GnRH agonist/antagonist will be provided from the site's pharmacy stock and administered in accordance with the prescribing information.

Concomitant Medication Restrictions or Requirements:

Required Concomitant Treatment

All subjects will be required to maintain ADT during study treatment, either using a GnRH agonist/antagonist or having a history of bilateral orchiectomy.

Prohibited Concomitant Treatments

The following medications are prohibited within 4 weeks of day 1 and during the study treatment period:

- 5 α-reductase inhibitors (finasteride, dutasteride);
- Estrogens;
- Cyproterone acetate;
- Abiraterone
- Biologic or other agents with antitumor activity against prostate cancer (with the exception of those therapies identified in inclusion/exclusion criteria);
- Systemic glucocorticoids greater than the equivalent of 10 mg per day of prednisone intended for the treatment of prostate cancer;
- Herbal medications that have known hormonal antiprostate cancer activity and/or are known to decrease PSA levels (i.e., saw palmetto);
- Androgens (testosterone, dehydroepiandrosterone, etc.);
- Investigational agents.

In addition, bisphosphonates and denosumab are prohibited unless stabilized for 2 weeks prior to day 1 and held constant throughout study treatment or administered for diagnosis of osteoporosis.

Enzalutamide Drug Interaction

There is a potential for enzalutamide to affect exposures to other medicinal products, or for other medicinal products to affect exposure to enzalutamide:

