5.1.3.4 Permitted Concomitant Treatment

The following treatments are allowed during the study (and do not require study drug discontinuation) including, but not limited to:

- Blood transfusions and growth factor support per SOC and institutional guidelines;
- Steroid use (for indication other than prostate cancer) per SOC;

- Pain therapy per SOC and institutional guidelines;
- Palliative radiation therapy including external beam radiotherapy or systemic radionuclides (e.g., Samarium or Strontium);
- Vaccine therapy that has prior market authorization and is not intended to treat prostate cancer;
- Palliative surgical procedures to treat skeletal-related events.

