5.4.2 Adverse Events

AE collection will begin at the time the informed consent form (ICF) is signed and continue until subject is determined to be ineligible for study entry, or initiation of new therapy for prostate cancer including commercial enzalutamide, or 30 days after the last dose of study drug, whichever occurs first.

See [Section 5.5 Adverse Events and Other Safety Aspects] for information regarding AE collection and data handling.

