5.5.5 Reporting of Serious Adverse Events (SAEs)

The collection of AEs and the expedited reporting of SAEs will start following receipt of the informed consent and will continue to safety follow-up visit.

In the case of a SAE, the investigator must contact delegated CRO by fax or email immediately (within 24 hours of awareness).

The investigator must complete and submit a SAE worksheet containing all information that is required by local and/or regional regulations to delegated CRO by email or fax immediately (within 24 hours of awareness).

For contact details, see [Section II Contact Details of Key Sponsor's Personnel]. Fax or email the SAE Worksheet to:

IQVIA RDS East Asia Pte. Ltd.

Lifecycle Safety

[contact] Email: [contact]

If there are any questions, or if clarification is needed regarding the SAE, please contact the sponsor's Medical Monitor/Study Physician or his/her designee [Section II Contact Details of Key Sponsor's Personnel].

Follow-up information for the event should be sent promptly (within 7 days of the initial notification).

Full details of the SAE should be recorded on the medical records, SAE Worksheet and on the (e)CRF.

The following minimum information is required:

- International Study Number (ISN)/Study number,
- Subject number, sex and age,
- The date of report,
- A description of the SAE (event, seriousness criteria),
- Causal relationship to the study drug (including reason), and
- The drug provided (if any)

The sponsor or sponsor's designee will submit expedited safety reports (e.g., IND Safety Reports, CIOMS-I) to Competent Authorities (CA) and concerned Ethics Committee (cEC) per current local regulations, and will inform the investigators of such regulatory reports as required. Investigators must submit safety reports as required by their IRB/local IEC within timelines set by regional regulations (e.g., EU, FDA) where required. Documentation of the submission to and receipt by the IRB/ local IEC of expedited safety reports should be retained by the site.

The sponsor or designee will notify all investigators responsible for ongoing clinical studies with the study drug of all SAEs which require submission per local requirements.

The heads of the study sites/investigators should provide written documentation of IRB/IEC notification for each report to the sponsor.

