6 DISCONTINUATION

6.1 **Discontinuation of Individual Subject(s)**

The subject is free to withdraw from the study treatment and/or study for any reason and at any time without giving reason for doing so and without penalty or prejudice. The Investigator is also free to terminate a subject's involvement in the study at any time if the subject's clinical condition warrants it.

Discontinuation Criteria from Study Drug Treatment for Individual Subjects:

- Any AE that is intolerable to the subject which cannot be ameliorated by the use of adequate medical intervention and/or dose reduction or that in the opinion of the Investigator would lead to undue risk to the subject if dosing is continued.
- Subject who experiences a seizure or any condition that significantly predisposes the subject to seizure such as brain metastasis or clinically evident stroke.
- Subject who experiences a confirmed event of PRES by brain imaging, preferably by MRI.
- Subject initiates an investigational agent or new therapy for prostate cancer.
- Subject who has evidence of radiological disease progression and/or PSA progression as confirmed by the Investigator and is no longer deriving clinical benefit. Imaging test can be done at the discretion of the investigator and are not part of the study.
- Subject has discontinued ADT (GnRH agonist/antagonist) and has a testosterone value in the noncastrate range (> 50 ng/dL).
- Subject who is, in the opinion of the Investigator or the Medical Monitor, non-compliant with the protocol requirements.
- Subject is lost to follow-up despite reasonable efforts by the Investigator to locate the subject.
- Subject withdraws consent for the study.

Subject will be discontinued from the 30 day study follow-up (Safety or Long-term Follow-up) if any of the following occur:

- Subject is lost to follow-up despite reasonable efforts by the Investigator to locate the subject.
- Subject withdraws consent for further follow-up.
- Death.
- Study termination by the Sponsor.

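### Adverse event collection can close while enzalutamide is still being taken: the new-therapy cut-off is not tied to the last dose, and the concomitant-treatment rules behind it do not fit together

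*Protocol*

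**What the plan says.** Six sets of rules bear on this point.

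- **Required.** Protocol 5.1.3.1: "All subjects are required to receive background therapy with ADT, either bilateral orchiectomy or a GnRH agonist or antagonist", to be kept up during study treatment. The synopsis files this under "Other Treatment for Prostate Cancer during the Study".
- **Prohibited.** Protocol 5.1.3.2, repeated in the synopsis and Appendix 12.1, bans "Biologic or other agents with antitumor activity against prostate cancer (with the exception of those therapies identified in inclusion/exclusion criteria"). A separate item bans systemic glucocorticoids above 10 mg/day prednisone equivalent when they are given for prostate cancer.
- **Permitted.** Protocol 5.1.3.4 is an open list of treatments that do not oblige the subject to stop study drug. It includes palliative systemic radionuclides, with samarium and strontium as examples, and "Steroid use (for indication other than prostate cancer) per SOC".
- **Stop rule.** Under Protocol 6.1, study drug is discontinued if "Subject initiates an investigational agent or new therapy for prostate cancer".
- **AE collection.** Under Protocol 5.4.2, for a subject who is not a screen failure, collection runs until "initiation of new therapy for prostate cancer including commercial enzalutamide, or 30 days after the last dose of study drug, whichever occurs first". Section 5.5.1 says the same. The Table 1 footnote names the same events without saying that the earliest governs. Section 5.5.5 says that AE collection and expedited SAE reporting "will continue to safety follow-up visit".
- **Deviations.** Protocol 8.1.6 makes it a major deviation to meet a withdrawal criterion and not be withdrawn (PD2), or to receive an excluded concomitant treatment (PD4). SAP 7.2.2 tabulates both, overall and by site.

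**The concern.** The exception to the ban points to criteria that do not list the treatments it would have to exempt. The phrase new therapy for prostate cancer carries a stop rule and an AE cut-off, yet it is never defined and never set against the permitted list. Sites must therefore decide for themselves whether a permitted treatment counts.

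The larger problem is the AE cut-off. It takes effect when new therapy starts and does not ask whether study drug has stopped. The nature, frequency and severity of AEs is the first primary endpoint (Protocol 2.3.1), so a window that can close during dosing affects what the trial exists to measure. PD2 and PD4 counts are exposed to the same ambiguity across about 7 centers.

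**Working it through.** The plan has no figure to reproduce here: the sample size of 50 has no power basis, and the question is whether the texts agree.

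**Step 1: is the exception empty?** In Protocol 3.2 and 3.3, inclusion 5 and exclusion 1 name enzalutamide. Orchiectomy appears in inclusion 7, but only as a ground of sterility. No criterion names a GnRH agent, a radionuclide or a steroid.

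**Step 2: each treatment against each rule.**

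| Treatment | Required or permitted | Ban (5.1.3.2) | Stop rule (6.1) | AE cut-off (5.4.2, 5.5.1) |
|---|---|---|---|---|
| Ongoing GnRH agonist or antagonist | Required, 5.1.3.1 | Not exempted on the literal text | Does not attach: not new | Does not attach: not new |
| Systemic radionuclide | Permitted, 5.1.3.4 | No carve-out; caught if held to have antitumor activity | Largely answered by 5.1.3.4 | No carve-out; depends on the reader |
| Steroid at or below 10 mg/day for prostate cancer | Not named; list is open | Outside the steroid item; general ban not excluded | Undetermined | Undetermined |

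**Step 3: when does the cut-off cost on-treatment data?** Let X be the day new therapy starts and Y the day of the last dose. Collection ends at the earlier of X and Y + 30. If X = Y, no on-treatment time is lost. If X < Y, collection ends at X, and Y − X days of dosing go uncollected. There are two routes to X < Y:

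- A subject receives a radionuclide and continues enzalutamide, as 5.1.3.4 allows, and the site reads the radionuclide as new therapy under 5.4.2.
- A subject starts new therapy and is not withdrawn at once, for example because the site learns of it late. PD2 exists for such cases.

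**Step 4: does anything downstream repair this?** SAP 6.2 counts as treatment-emergent any AE after the first dose, with no end date, so it can use only what was collected. Protocol 5.5.6 asks for notice of later events, but only those the investigator thinks may be related to study drug or study participation. That cannot restore overall frequency and severity. The SAP gives no rule for reading PD2 or PD4.

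**Step 5: size per subject.** At the planned 50, one subject is 1/50 = 2% of the denominator. One subject whose AE is missed, or whose deviation is coded differently, moves that percentage by 2 points.

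**The case against.** The strongest reply is that losing on-treatment AEs needs an inconsistent reading: a site that calls a treatment new therapy must, by 6.1, stop enzalutamide too, and then X = Y. This holds for a compliant site that acts the same day. It does not cover late discovery or PD2 cases. Nor does it cover radionuclides, where 5.1.3.4 addresses stopping study drug and is silent on AE collection. One can argue that the permission should carry over to 5.4.2, but nothing there says so.

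Several stronger readings are tempting, and the documents do not support them.

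- **Every man on a GnRH drug becomes a PD4 case.** This follows only from the literal text. Section 5.1.3.1 requires the treatment by name, and 6.1 makes stopping it, with noncastrate testosterone, a ground for discontinuation. The intent is clear. The criteria also defer to local prescribing information, which was not available and may name androgen deprivation.
- **Low-dose steroids for prostate cancer are allowed in one place and banned in another.** No section requires or expressly allows them. This is a gap and not a contradiction.
- **Samarium and strontium are plainly banned.** The documents do not say that they have antitumor activity. The survival benefit reported in Protocol 1.1 is for radium-223.
- **Section 5.5.5 contradicts 5.4.2.** The safety follow-up visit is itself set by the last dose or the start of new therapy, whichever is earlier (synopsis, 2.2.1). Apart from visit timing, the two largely agree.

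**Conclusion.** The point holds in a limited form. The exception's cross-reference does not work, the new-therapy term is undefined, and the AE cut-off can precede the last dose. The last of these matters most, because it can remove on-treatment data from the primary endpoint.

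A reader might want to put a number on the subjects affected, or on the length of follow-up lost. The documents give no frequency for radionuclide use, late-discovered therapy or delayed withdrawal, so any share would be invented. The loss per subject is Y − X days, which may be short. Only the weight of one subject is known: 2 percentage points, assuming 50 treated.

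The effect on deviation counts is descriptive. Neither the FAS nor the SAF depends on deviations, and no per-protocol set is defined. The conclusion rests on the text of the protocol and SAP alone.

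**What to change.** (a) In Protocol 5.4.2, 5.5.1 and the Table 1 footnote, state that AE collection does not end before the last dose of study drug, and apply the new-therapy cut-off only after that dose. This is a data-collection rule and leaves treatment decisions untouched. The cost is longer AE collection in a few subjects, with no added visits.

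(b) Reconcile 5.1.3.1, 5.1.3.2, 5.1.3.4, 6.1, the synopsis and Appendix 12.1. Repair the exception's cross-reference, and define new therapy for prostate cancer. The definition should say how permitted treatments, and steroids at or below the stated limit given for prostate cancer, are classified, so that PD2 and PD4 are coded the same way at every site. The cost is protocol wording.

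Whether the permission or the prohibition prevails for any treatment is a clinical decision for the sponsor. A blanket exemption for everything in 5.1.3.4 would make that decision, so it is not proposed here.

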5.1.3.3 Enzalutamide Drug Interaction

There is a potential for enzalutamide to affect exposures to other medicinal products, or for other medicinal products to affect exposure to enzalutamide:

- Strong CYP2C8 inhibitors (e.g., gemfibrozil) are to be avoided. If subject must be coadministered a strong CYP2C8 inhibitor, the dose of enzalutamide should be reduced to 80 mg once daily. If coadministration of the strong inhibitor is discontinued, the enzalutamide dose should be returned to the dose used prior to initiation of the strong CYP2C8 inhibitor.
- Strong CYP3A4 inducers (e.g., carbamazepine, phenobarbital, phenytoin, rifampin) or moderate CYP3A4 inducers (e.g., bosentan, efavirenz, etravirine, modafinil, nafcillin, St. John's Wort) should be avoided if possible as they may reduce enzalutamide plasma concentration if coadministered. Selection of a concomitant medication with no or minimal CYP3A4 induction potential is recommended.
- Enzalutamide is a strong inducer of CYP3A4 and a moderate inducer of CYP2C9 and CYP2C19. Medicinal products with a narrow therapeutic range that are substrates of CYP3A4 (e.g., alfentanil, cyclosporine, dihydroergotamine, ergotamine, fentanyl, pimozide, quinidine, sirolimus, tacrolimus), CYP2C9 (e.g., phenytoin, warfarin), or CYP2C19, or UGT1A1 (e.g., S-mephenytoin) should be avoided if possible, as enzalutamide may decrease their exposure.
- If enzalutamide coadministration with warfarin cannot be avoided, additional international normalized ratio (INR) monitoring should be conducted.
- Enzalutamide is an inhibitor of human P-glycoprotein (P-gp) and may increase exposure to medicines that are P-gp substrates. Medicinal products with a narrow therapeutic range that are substrates for P-gp (e.g., digoxin, colchicine, dabigatran etexilate) should be used with caution when administered concomitantly with enzalutamide.

